1.2. Secondary, exploratory objectives

- 1.2.1. To evaluate the safety of convalescent plasma (CP) administration in hospitalized COVID-19 patients
- 1.2.2. To evaluate viral shedding of SARSCoV-2 in nasopharyngeal or nasal samples before and on days 3, 7, and 14 after CP transfusion
- 1.2.3. To perform genomic analysis of the SARS-CoV-2 from patients before and after treatment with CP transfusion
- 1.2.4. Determine cumulative incidence of disease severity (transfer to ICU, type of respiratory support, LOS, and mortality)

2. Background

Passive antibody treatment involves the administration of antibodies against a specific infection to a susceptible individual to treat or ameliorate the severity of the disease caused by the infectious agent. Plasma from patients that have recovered from the infection is harvested and administered to the non-immune. The use of this modality of treatment dates back to the 1890's, but its popularity decreased during the antibiotic era.(Casadevall, 2020)

During the current SARSCoV-2 pandemic, with its associated high mortality and morbidity and the lack of demonstrated and effective treatment or vaccine, the induction of immunity with the transfusion of convalescent plasma offers a therapeutic alternative.

Convalescent plasma was studied during the SARS epidemic in 80 patients in Hong Kong.(Cheng 2005) Those treated before day 14 had improved prognosis defined by discharge from hospital before day 22, consistent with the notion that earlier administration is more likely to be effective. There is also anecdotal information on the use of convalescent serum in seriously ill individuals. Three patients with SARS in Taiwan were treated with 500 mL convalescent serum, resulting in a reduction in serum virus titer, and each survived (Yeh 2005)

PROTOCOL TITLE: Open, non-comparative pilot study to provide access to treatment with investigational convalescent plasma and measure antibody levels in patients hospitalized with COVID-19

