3. Contraindication to transfusion or history of prior severe allergic reactions to transfused blood products
4. On ECMO or in refractory shock at entry

5. Number of Subjects

This pilot aims to explore safety and measure antibody levels in patients treated with CP. We aim to enroll 30 subjects to ensure the estimate of *neutralizing antibodies* to be within 20% margin of error.

PROTOCOL TITLE: Open, non-comparative pilot study to provide access to treatment with investigational convalescent plasma and measure antibody levels in patients hospitalized with COVID-19

6. Study Timelines

Hospitalized patients will be enrolled as soon as their COVID-19 diagnosis is confirmed, using approved diagnostic methods, and will be followed until hospital discharge or death. Patient enrollment will start immediately after IRB approval. We anticipate a 3-month enrollment. The study will continue for another 24-months after the last enrollment during which we will be able to process and analyze data, and disseminate findings.

7. Study Endpoints

7.1. Primary endpoint:

- 7.1.1. Titers of SARS-CoV-2 neutralizing antibodies measured by focus reduction neutralization test (FRNT) at days 0 (pre-transfusion), 1, 3, 7 and 14 days of CP transfusion.

- 7.1.2. Availability of convalescent plasma

7.2. Secondary endpoints:

Clinical outcomes:

- 7.2.1 Serious adverse events
- 7.2.2 SARCoV-2 viral shedding in nasopharyngeal samples determined by RT-PCR
- 7.2.3 Genomic variations of SARS-CoV-2 before and after CP transfusion
- 7.2.4 Transfer to ICU
- 7.2.5 Type and duration of respiratory support (and other ICU support including ECMO, CRRT) in ICU
- 7.2.6 Cardio-circulatory arrest (at any time)
- 7.2.7 ICU mortality and LOS
- 7.2.8 Hospital mortality and LOS
- 7.2.9 Ventilator-free days
- 7.2.10 In hospital mortality
- 7.2.11 Titer of other functions of antibodies, including antibody-dependent cell-mediated and complement-dependent cytotoxicity

7.3. Safety Endpoints:

- 7.3.1 Rapid deterioration of respiratory or clinical status on transfusion of SARS-CoV-2 convalescent plasma.
- 7.3.2 Cumulative incidence of serious adverse events during the study period: febrile non-hemolytic transfusion reaction, allergic transfusion reaction, transfusion related acute lung injury (TRALI), transfusion associated circulatory overload (TACO),

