 - 12.5.2. The anti-SARS-CoV-2 convalescent plasma will be in standard plasma blood unit bags, anticoagulated with a citrate-based anticoagulant (ACD-A, CP2D, et cetera), labeled with a specific ISBT product code, and stored in the UNM Blood Bank per FDA, AABB, and CAP protocols. Plasma transfusion will be administered over no more than four hours.

Table 1: Schedule of Events

PROTOCOL TITLE: Open, non-comparative pilot study to provide access to treatment with investigational convalescent plasma and measure antibody levels in patients hospitalized with COVID-19

Study period	Screen	Baseline	Transfusion	Follow-up			
Day	-1 to 0	0	0	1	3	7	14
Eligibility							
Informed consent	x						
Demographic and Medical history	x						
SARS-CoV-2 RT-PCR for eligibility	x						
Pregnancy test	x						
Type and screen	x						
Study Agent Administration							
Plasma Transfusion			x				
Study Procedures							
Vital signs	x	x	xxxx[1]	x	x	x	x
Physical assessment	x		x	x		x	
Symptom screen	x	x	x	x	x	x	x
Concomitant medications	x	x	x				

PROTOCOL TITLE: Open, non-comparative pilot study to provide access to treatment with investigational convalescent plasma and measure antibody levels in patients hospitalized with COVID-19

Adverse event monitoring		x	x	x	x	x	x	
Laboratory testing								
SARS-CoV-2 RT-PCR^[2] and Genomic analysis		x			x	x	x	
SARS-CoV-2 neutralizing antibody		x		x	x	x	x	
Secondary End point registration (clinical outcome)								

1. Vital sign testing: Immediately prior to infusion, 10-20 minutes after start of infusion, at completion of infusion and 30-60 minutes after the end of the infusion
2. Sampling can include nasopharyngeal, nasal or oropharyngeal swabs.

13. Data Analysis

13.1.1. We will determine whether there is a correlation between the NAb dose (in NAb units/kg body weight, where a unit is the reciprocal of the endpoint NAB titer in the CP multiplied by the volume in ml) and change or lack of change when comparing pre-treatment and day one NAb titers. We will also compare changes in pre- and post-treatment NAb titers based on NAb dosing calculated in units/BSA and units/calculated plasma volume to see if either measurement provides a better prediction of changes in NAb titers in recipients.

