13.2. Data analysis will be limited to hospitalized subjects with respiratory symptoms and laboratory confirmation of SARS-CoV-2 infection by detection RNA in upper or lower respiratory samples (nasal or oral swabs or endotracheal fluid) or blood or by detection of NAb in serum. Subjects without laboratory-confirmed COVID 19 will be excluded from analysis.

Neutralizing antibody titers in the patient's first blood sample (day 0) will be compared by rank sum (Wilcoxon) test between patients who develop any of the secondary

PROTOCOL TITLE: Open, non-comparative pilot study to provide access to treatment with investigational convalescent plasma and measure antibody levels in patients hospitalized with COVID-19

clinical end-points and patients who do not develop these secondary endpoints. The same comparison will be performed to evaluate NAb titers with other parameters such as age ≥ 65 and < 65 , presence or absence of diabetes, or presence or absence hydroxychloroquine therapy. These analyses of day 0 NAb titers aim to characterize patient heterogeneity in NAb titers in relationship to patient demographic and clinical characteristics.

We will also analyze the association between NAb titers at day 0 with duration of viral shedding, duration of hospitalization and duration of intubation and other clinical parameters.

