Our primary endpoint for statistical analysis is changes in NAb titers at day 1, 3, 7, and 14 from the entry level (day 0). Our primary hypothesis is that NAb titers will increase post-transfusion in positive correlation with transfused volume of convalescent plasma when adjusted for NAb titer in the convalescent plasma. We will use repeated measurements analysis of variance (ANOVA) or analysis of covariance (ANCOVA) when controlling for other factors (e.g. use of hydroxychloroquine) for initial exploration of the association with the transfusion volume of convalescent plasma. A more advanced approach is to use nonlinear regression models with random effects to characterize the trajectory of NAb titers over the course of 14 days. This latter approach can effectively characterize individual-specific trajectory in NAb titers in relation to convalescent plasma, and at the same time quantify between-patients variation, thereby improving statistical power. This mixed-effects nonlinear regression modeling approach is also capable of adjusting for other factors as appropriate (e.g. patient age). We will also conduct post-hoc analysis of change in NAb titers from day 0 to a specific day (day 1, 3, 7, or 14) post transfusion of convalescent plasma when appropriate. Better understanding and better characterization of the relationship between NAb titers and amount of convalescent plasma transfusion adjusted for NAb titer in the convalescent plasma will inform standardized dosage for future study.

In the absence of a comparison group, we will use descriptive statistics to report other parameters of interest (e.g. secondary outcomes), including the use of mean (SD), frequency (%) and their confidence interval. When appropriate, we will also report association between a parameter of interest and a factor of clinical relevance (e.g. duration of shading and underlying comorbidities, NAb titers at a specific post-transfusion day and underlying comorbidities, NAb titers at a specific post-transfusion day and secondary outcomes such as transfer to ICU or hospital death). This analysis will utilize odds ratio and Fisher's test for dichotomous variables, and Wilcoxon test a continuous variable.

We will conduct interim analysis after the first 10 patients complete the study. Based on the interim analysis results we may consider submitting a protocol amendment requesting adjustment our patient recruitment or CP dosing.

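### Viral shedding duration is interval- and right-censored, but the plan names no censoring method; if swabs are lost at discharge, the derived duration will track length of stay

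*Combined protocol and SAP*

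**What the plan says.** Objective 1.2.2 schedules respiratory swabs "before and on days 3, 7, and 14 after CP transfusion". The Table 1 row "SARS-CoV-2 RT-PCR^[2] and Genomic analysis" agrees: one baseline mark, then days 3, 7 and 14. Under section 6, patients "will be followed until hospital discharge or death". Section 21.2 places study procedures in the participant's room or another private area of the hospital, and no swab after discharge is described.

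Endpoint 7.2.2 is "SARCoV-2 viral shedding in nasopharyngeal samples determined by RT-PCR". It does not mention duration. Duration first appears in section 13.2, which plans to study the "association between NAb titers at day 0 with duration of viral shedding, duration of hospitalization and duration of intubation" and names no method for this. Later in 13.2, "duration of shading and underlying comorbidities" (evidently shedding) is given as an example of an association to be reported, and the tools for such associations are "odds ratio and Fisher's test for dichotomous variables, and Wilcoxon test a continuous variable".

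The text gives no start or end rule for shedding duration, no rule for a patient still positive at the last swab, and no handling of death or missed swabs.

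**The concern.** A swab schedule does not show the day of clearance. It shows an interval between the last positive and first negative swab or, if no negative is seen, only a lower limit. A Wilcoxon test on one derived number per patient has to give the second group some value. The obvious choice is the last positive day, and that day cannot exceed the length of stay if swabbing ends at discharge.

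The derived duration would then partly measure stay. Section 13.2 relates day-0 NAb titer to both shedding duration and hospital stay, so two apparent findings could be one. Comorbidities are also plausibly related to stay. Section 2 asks whether antibody levels go with viral clearance and notes that viral presence matters for transmission in hospital, so a discharge effect read as a viral effect would mislead on a question the protocol itself raises. The false discovery rate adjustment in section 13.2 deals with multiplicity and does not remove this bias.

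**Working it through.** The documents give no figure for shedding time or length of stay, so there is nothing to reproduce.

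**Inputs from the documents.** Swab days 0, 3, 7 and 14 (1.2.2, Table 1); follow-up to discharge or death (section 6); 30 patients (section 5).

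**Assumptions.** Clearance time T from transfusion is lognormal with median 8 days and log-SD 0.6. Stay L is lognormal with median 7 or 14 days and log-SD 0.6. T and L are independent, PCR is error-free and all patients are positive on day 0. Ranges below use clearance medians of 5 to 12 days and stay medians of 5 to 14 days.

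**Step 1: what is observable.** Clearance falls in (0,3], (3,7] or (7,14], or is right-censored at the last swab.

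**Step 2: probabilities.**
- P(T > v) = 1 − Φ(ln(v/8)/0.6) = 0.949, 0.588 and 0.176 at days 3, 7 and 14. The true mean is 8 × exp(0.6²/2) = 9.58 days.
- P(L ≥ v), median stay 7: 0.921, 0.500, 0.124. Median stay 14: 0.995, 0.876, 0.500.

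**Step 3: share right-censored if swabs stop at discharge.** Sum, over the last swab taken, of P(last swab on day v) × P(T > v):
- Stay median 7: 0.079 + 0.421 × 0.949 + 0.376 × 0.588 + 0.124 × 0.176 = 0.72.
- Stay median 14: 0.005 + 0.119 × 0.949 + 0.376 × 0.588 + 0.500 × 0.176 = 0.43.
- All swabs taken: P(T > 14) = 0.18.

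Over the ranges, 23% to 92% are censored if swabs stop at discharge, and 4% to 40% if all are taken.

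**Step 4: mean derived duration.**
- Last-positive rule: 3·P(L≥3)P(T>3) + 4·P(L≥7)P(T>7) + 7·P(L≥14)P(T>14).
- First-negative rule (last positive if no negative is seen): add 3·P(L≥3)P(T≤3) + 4·P(L≥7)P(3<T≤7) + 7·P(L≥14)P(7<T≤14), where the three clearance probabilities are 0.051, 0.361 and 0.412.

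| Swabs | Last positive | First negative | True mean |
|---|---|---|---|
| Stop at discharge, median stay 7 | 2.62 + 1.18 + 0.15 = 3.95 | 3.95 + 1.22 = 5.17 | 9.58 |
| Stop at discharge, median stay 14 | 2.83 + 2.06 + 0.62 = 5.51 | 5.51 + 2.86 = 8.37 | 9.58 |
| All taken to day 14 | 2.85 + 2.35 + 1.23 = 6.43 | 6.43 + 4.48 = 10.91 | 9.58 |

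Two groups with identical clearance but median stays of 7 and 14 days thus differ by 5.51 − 3.95 = 1.56 days under one rule and 8.37 − 5.17 = 3.20 under the other.

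Over three clearance medians, four stay medians and three rules (last positive, midpoint, first negative), the mean was too short in 35 of 36 combinations when swabs stopped at discharge. The exception was +0.8 days (clearance median 5, stay median 14, first negative).

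**Step 5: effect on the test (simulation, 15 v 15, nominal 5%, identical clearance, median 8).**
- Median stays 7 v 14 days: about 25% rejections (last positive) and 64% (first negative). Repeat runs differed by about one point.
- Median stays 7 v 10 days: 12% and 25%.
- All swabs taken, patients still positive at day 14 ranked last: 4.2% to 4.5%.

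Although clearance and stay were independent, the Spearman correlation of derived duration with stay was 0.10 to 0.85 (last positive) and 0.42 to 0.92 (first negative).

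**The case against.** The strongest reply is that much of the difficulty is inferred. A reader might take the plan to treat duration as exact, to stop swabbing at discharge, and to test day-0 NAb titer against duration by Wilcoxon. The documents say none of these. Table 1 carries the PCR row to day 14 without exception, no last-positive or first-negative rule is adopted, and the NAb comparison has no named method. Loss of swabs at discharge is a probable consequence of the follow-up rule and the in-hospital setting, not a stated intention. This part of the reply stands.

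A reader might also infer that the gaps between swabs invalidate Wilcoxon. They do not. The test uses ranks and tolerates ties, and on a complete common schedule the outcomes form ordered classes; its size was 4.2% to 4.5%. The damage comes from swabs lost to discharge or death.

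The reply also has force against the remedy. Turnbull and standard interval-censored models assume non-informative censoring. If log stay and log clearance correlate at 0.5 (an assumption), the proportion negative at day 7 among those still swabbed is 27% to 32% against a true 41%. Observed clearances are also few. With clearance median 8, stay medians of 8 to 12 days and a wider spread of stays (log-SD 0.8), 35% to 49% of patients have an observed negative, or about 10 to 15 of 30. A parametric regression on so few is fragile.

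Finally, 1.2 labels these objectives exploratory, and 13.2 disclaims power for all analyses and puts the focus on the primary antibody outcome. That limits severity. It does not supply the missing definition or the missing method for censored values.

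**Conclusion.** The point holds in this form: shedding duration is undefined, interval-censored by the schedule and right-censored in patients still positive at their last swab, and neither planned use of it allows for that. If swabs are lost at discharge or death, derived durations will mostly be too short and will track stay. The false-positive rates of about 25% and 64% illustrate this for stays of 7 v 14 days. They are not predictions, and they fall when the groups differ less in stay or when stays are more widely spread.

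It would go too far to say that durations must be biased short. With all swabs taken and clearance median 8, the last-positive rule gives 6.4 days and the first-negative rule 10.9, against a true 9.6. In that case Wilcoxon also remains valid.

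Every size rests on assumed distributions, independence of stay and clearance, and error-free PCR. If discharge depended on clearance, the bias would differ. Severity is minor to moderate: the analysis is secondary and exploratory, and the primary NAb analysis does not use shedding duration.

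**What to change.** In section 13.2:

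1. Define duration from transfusion to PCR negativity. State what counts as negativity (one negative swab or a confirmed one) and what is done with a patient already negative at the day-0 swab. State whether swabs are sought after discharge.
2. Treat the time as interval-censored between last positive and first negative swab, and right-censored at the last swab if still positive. Estimate the distribution by Turnbull's method. Replace Wilcoxon with an interval-censored group comparison for comorbidities, and name an interval-censored regression for day-0 NAb titer. Any parametric model such as Weibull should be a sensitivity analysis only.
3. Treat death separately, and report the number of patients who died while still positive.
4. Report the proportion PCR-negative at days 3, 7 and 14, with the number swabbed at each. The frequency and confidence interval wording in 13.2 already permits this.
5. State that censoring by discharge may be informative, so that neither the Turnbull estimate nor the per-visit proportions are read as free of that bias.

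The cost is a few sentences and slightly more analysis work, with no new samples. Intervals will be wider, which reflects what the swabs can show. Settling the rule before the data are seen also prevents its being chosen afterwards.

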PROTOCOL TITLE: Open, non-comparative pilot study to provide access to treatment with investigational convalescent plasma and measure antibody levels in patients hospitalized with COVID-19

transfusion related infection, hemolytic transfusion reaction or evidence of antibody dependent enhancement of infection (ADE).

8. Research Setting

The study will be conducted in the University of New Mexico Hospital. Patients admitted to the COVID-19 units including the emergency department, regular wards and intensive care units will be enrolled. Patients will be identified from the TriCore Laboratory testing result portal available to the research team or upon notification by providers in the participating institutions. Approval by the treating provider will be requested before patient enrollment and consent.

There is no external sponsor for this research. Immune assays and genomic studies will be performed utilizing existing resources within the [name] and [name] laboratories in the Center for Global Health.

SARS-CoV-2 neutralizing antibody titers will be measured using the focus reduction neutralization test (FRNT) in [name] Laboratory, Center for Global Health (CGH), UNMHSC. Neutralization assays will be conducted using methods already established in the [name] laboratory. Briefly, serial dilutions of plasma will be incubated with 50-100 pfu of SARS-CoV-2 at equal volumes for 1 hour and added to Vero E6 cells, followed by overlaying with agarose. Two days later cells will be fixed with 4% formaldehyde, stained with crystal violet, and plaques will be counted. Other functions of antibody, including antibody-dependent cell-mediated cytotoxicity and complement-dependent cytotoxicity, will be ascertained using established methods.

Virus sequencing will be performed in the laboratory of [name] in the Center for Global Health using the PCR-based NGS sequencing protocol described by the ARTIC Network <https://artic.network/ncov-2019>

9. Resources Available

9.1. Principal investigator and co-investigators are experienced Pulmonary, Critical Care, Infectious Disease ID Pharmacists, Virologist or Transfusion Medicine specialists with ample experience in conducting clinical trial and with the use of CP in previous clinical studies (GM):

- 9.1.1. [name], is a Pulmonary and Critical Care Medicine specialist and is the Chief of the Division of Pulmonary at UNMH
- 9.1.2. [name], is an Infectious Disease Attending and is the Chief of Infectious Diseases at UNMH.

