PROTOCOL TITLE: Open, non-comparative pilot study to provide access to treatment with investigational convalescent plasma and measure antibody levels in patients hospitalized with COVID-19

Given that we have a large number of clinical parameters of potential interest and a small sample of 30 patients, we do not have the statistical power or data depth for all analyses. The focus of our analysis is on the primary outcome and primary hypothesis. Much of the analyses of secondary outcomes are of the nature of exploration. We will adjust for multiplicity of comparisons (e.g. associations) using False Discovery Rate (FDR) in reporting our findings.

13.3. Sample size. A sample size determination is less plausible for this pilot study since we aim to establish the effect size of convalescent plasma transfusion on Nab titers.

However, we will conduct a post-hoc statistical power analysis to determine the actual power with the sample we obtain.

14. Provisions to Monitor the Data to Ensure the Safety of Subjects

14.1. A DSMB will be convened to include clinicians specializing in clinical trials, transfusion medicine and biostatisticians. The roster will be provided in a Modification for HRRC approval once the DSMB has been created.

14.2. The safety information that will be collected and monitored as follows: reports of rapid deterioration of respiratory or clinical status on transfusion of SARS-CoV-2 convalescent plasma and cumulative incidence of serious adverse events during the study period: febrile non-hemolytic transfusion reaction, allergic transfusion reaction, transfusion related acute lung injury (TRALI), transfusion associated circulatory overload (TACO), transfusion related infection, and hemolytic transfusion reaction.

14.3. Review of data after 10 participants have been enrolled.

14.4. Considering the novelty and rapidly changing situation of the COVID-19 pandemic, the investigators will review relevant publications that may help inform decisions related to the efficacy and safety of the investigational products.

14.5. The occurrence of any serious adverse event will be notified to the HRRC in accordance with GCP regulations. An analysis of all adverse events will be presented with the analysis of the first 10 patients enrolled and periodically thereafter.

14.6. The conditions that would trigger a suspension or termination of the research (i.e., stopping rules), are as follows:

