a. If available published information convincingly reports non-efficacy or significant safety concerns with the use of SARS-CoV-2 convalescent plasma.

b. If an unexpectedly high incidence of serious adverse events judged to be related to SARS-CoV-2 convalescent plasma is detected in these critically ill COVID-19 patients during the trial in the clinical judgement of the investigators compared to that expected in similarly ill patients receiving normal donor plasma in the clinical judgement of the investigators.

PROTOCOL TITLE: Open, non-comparative pilot study to provide access to treatment with investigational convalescent plasma and measure antibody levels in patients hospitalized with COVID-19

- c. If there is an unanticipated safety signal, stopping the study will be considered.

14.7. Findings will be reported to the HRRC within 5 business days and to the FDA accordingly. A preliminary analysis of the study end points will be performed after 10 patients have been enrolled and end-points reached. The results will be presented to the HRRC and investigators.

15. Withdrawal of Subjects

15.1. Subjects will be withdrawn if the PI determines, in consultation with the treating clinician(s) that continuation in the study is not in the participant's best interest. Subjects may also withdraw (or be withdrawn by their LAR at their request at any time during their participation in the study by contacting a member of the study team.

15.2. If a patient develops a serious adverse event that may be probably or definitely related to the CP, during the infusion, that may trigger the discontinuation of the offending drug.

15.3. If a participant is withdrawn from the study, chart review will continue to be performed to track the participant's clinical outcomes.

15.4. Data and specimens collected before withdrawal will not be removed from the study.

16. Data Management/Confidentiality

16.1. Participants will be assigned a randomly generated study ID that will be linked to identifiers (MRN, DOB) in a linking table to be kept separate from the research data. Data and specimens will be labelled with the study ID only.

16.2. Only HRRC-approved members of the study team who have the appropriate training will have access to the data and identifiers.

16.3. Data will be entered into REDCap on a password-protected computer using a secure network.

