A key potential benefit is treatment for established infection. Convalescent plasma would be administered to those with clinical disease in an effort to reduce their symptoms and mortality. Based on the historical experience with antibody administration, it can be anticipated that *antibody administration relatively early in the course of disease would be more effective in preventing disease progression than in the treatment of established severe disease.*

Given that historical and current anecdotal data on use of convalescent plasma suggest it is safe in coronavirus infection, the high mortality of COVID-19, particularly in elderly and vulnerable persons, suggests that the benefits of its use in those at high risk for or with early disease outweigh the risks. However, for all cases where convalescent plasma administration is considered, a risk-benefit assessment must be conducted to assess individual variables.

20. Recruitment Methods

Members of the research team will review the list of admitted or hospitalized patients with a positive SARS-CoV-2 test. Alternatively, treating providers may also notify the research team of the admission of SARS-CoV-2 patients or the positive result of a suspected COVID-19 patient.

21. Provisions to Protect the Privacy Interests of Subjects

- 21.1.** Only members of the research team will access trial related documents.
- 21.2.** All study procedures will be conducted in the participant's room or other private area of the hospital.

22. Economic Burden to Subjects

PROTOCOL TITLE: Open, non-comparative pilot study to provide access to treatment with investigational convalescent plasma and measure antibody levels in patients hospitalized with COVID-19

- 22.1. The study is responsible for the cost of any research-related procedures. The participant and/or third party payer is responsible for any standard of care procedures.
- 22.2. Investigators do not anticipate any additional costs.

23. Compensation

No compensation will be given to study participants.

24. Compensation for Research-Related Injury

The University of New Mexico does not have funds set aside to pay for the cost of any care or treatment that might be necessary or for any wages lost as a result of participating in this study. Medical costs to care and treatment of study related harm will be billed to the participant and/or third party payer.

25. Consent Process

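### Section 6 ends follow-up at discharge while Table 1 monitors adverse events to day 14, so the observation time behind the cumulative SAE incidence can depend on discharge date

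*Combined protocol and SAP*

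**What the plan says.** Section 6 (Study Timelines) gives no fixed day for the end of follow-up: patients "will be followed until hospital discharge or death".

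Table 1 (Schedule of Events) has a row for "Adverse event monitoring" marked at baseline, at transfusion and on days 1, 3, 7 and 14. Its header row is labelled *Study period* and runs from screening to day 14. The two footnotes concern vital-sign timing and swab type. Neither makes the later visits conditional on the patient still being in hospital.

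Endpoint 7.3.2 is "Cumulative incidence of serious adverse events during the study period", and section 14.2 repeats it as an item for safety monitoring. Neither place gives the period in days. The list in 7.3.2 has seven event types and includes ADE; the list in 14.2 does not.

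Section 13.2 plans descriptive statistics for outcomes other than the primary, "including the use of mean (SD), frequency (%) and their confidence interval". It states no denominator and no rule for patients who leave before day 14.

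Section 21.2 says: "All study procedures will be conducted in the participant's room or other private area of the hospital". Section 15.3 provides for continued tracking, but only in one case: "If a participant is withdrawn from the study, chart review will continue to be performed".

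**The concern.** Sections 6 and 12 give different ends to observation. Under section 6, a patient discharged on day 5 is no longer followed when the day 7 and day 14 checks fall due. Under Table 1 those checks are still required, but the plan names no means of doing them: procedures take place in hospital, and chart review is provided for withdrawn participants, not discharged ones.

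A cumulative incidence needs the same period at risk for everyone, or an analysis that allows for unequal periods. Here the period would be set by discharge, which is itself related to prognosis. If the result is a plain percentage of all enrolled, SAEs after discharge drop out of the numerator while the patients stay in the denominator.

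Safety is objective 1.2.1 and one of the two aims given for the pilot in section 5. Three of the seven event types in 7.3.2 (infection, hemolytic reaction, ADE) need not appear around the infusion, and section 18.2 asks for vigilance about ADE in particular. These are the events that a stay-limited observation is most likely to miss.

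**Working it through.** The plan states no SAE rate, length of stay or discharge proportion, so it has no figure of its own to reproduce on this point. The check has two parts.

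**1. The passages side by side**

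| Patient | Section 6 | Table 1 | Means of observation described |
|---|---|---|---|
| Discharged day 5 | Follow-up ends day 5 | Checks due days 7 and 14 | None after discharge |
| In hospital to day 14 | Followed | Checked to day 14 | In hospital |
| In hospital to day 30 | Followed to day 30 | No scheduled check after day 14 | In hospital |

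The two sections agree only for a patient whose follow-up ends at day 14. The first row can lose events. In the third row events are still observable, but it is unclear whether an SAE on day 20 counts towards 7.3.2.

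**2. How much could be lost (illustration; every input except n = 30 is assumed)**

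- True 14-day SAE risk p = 0.20, that is 0.20 × 30 = 6 expected events.
- Share *a* of events occurs within 24 hours; the rest are spread evenly over days 1 to 14 (13 days).
- Share *q* of patients is discharged on day *D*; the others stay to day 14 or longer.
- Nothing is ascertained after discharge, the denominator stays at 30, and discharged patients carry the same risk as the others.

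Missed share = (1 − a) × q × (14 − D)/13. Observed risk = p × (1 − missed share).

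With a = 0.5, q = 0.5, D = 7: missed share = 0.5 × 0.5 × 7/13 = 0.135; observed risk = 0.20 × 0.865 = 17.3%; missed events = 6 × 0.135 = 0.81.

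Largest loss, a = 0, q = 0.7, D = 5: missed share = 0.7 × 9/13 = 0.485; observed risk = 10.3%; missed events = 2.9.

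Over q = 0.3 to 0.7 and D = 5 to 10:

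| Share of events within 24 h | Observed risk (true 20%) | Expected events missed, of 6 |
|---|---|---|
| 100% | 20.0% | 0 |
| 80% | 18.1-19.6% | 0.1-0.6 |
| 50% | 15.2-19.1% | 0.3-1.5 |
| 0% | 10.3-18.2% | 0.6-2.9 |

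For scale, the exact 95% confidence interval for 6/30 is 7.7-38.6%, and for 3/30 it is 2.1-26.5%.

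The unstated denominator matters as well. With 3 events and 15 patients discharged event-free before day 14, the result is 3/30 = 10% or, among the 30 − 15 = 15 others, 3/15 = 20%. The first can be too low, because later events in the 15 are unseen. The second can be too high, because it drops patients for having left without an event.

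**The case against.** The strongest reply is that the window is not really missing. The header of Table 1 carries the same term that 7.3.2 uses and runs to day 14, and 12.4 refers to that table for the protocol activities. This largely stands: day 14 is the natural reading, and it would be too much to say that the plan has no common window at all. But a column label does not override the explicit statement in section 6, and it does not say how a discharged patient is to be observed.

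Second, section 14.5 requires any SAE to be notified, with no day limit. That answers the worry about patients in hospital beyond day 14. It does not help after discharge, since the team must first learn of the event.

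Third, the effect may be small. Febrile and allergic reactions, TRALI and TACO make up four of the seven listed types and may cluster near the infusion (an assumption; the documents give no onset times). Patients sent home early may also be at lower risk than the illustration supposes. Against the width of an interval from 30 patients, most rows of the table are modest. All of this stands and limits the size, not the existence, of the problem.

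Three stronger readings are tempting and are not supported:

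- A reader might infer that the plan counts early-discharged patients as event-free. That would follow from a crude percentage over all 30, but section 13.2 is silent on denominator and censoring.
- A reader might infer that stopping rule 14.6b fails for want of a comparable rate. That rule rests on the investigators' clinical judgement and sets no numerical comparison.
- A reader might assume a length of stay and present the share leaving before day 14 as the bias. That measures early discharge, not missed SAEs.

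**Conclusion.** The point holds as an inconsistency with a possible downward bias of unknown size. Section 6 and Table 1 disagree on when observation ends, and no visible text provides for observation after discharge. If section 6 is followed and a crude percentage over all enrolled is reported, SAEs arising after discharge could be understated.

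The documents do not allow the size to be fixed. In the illustration it runs from nothing, when all events fall within 24 hours, to about half of a true 20% risk in the most unfavourable corner. Those figures rest on the assumed risk, timing and discharge pattern and are not estimates for this trial.

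Safety is a secondary, exploratory objective reported descriptively in a single arm of 30, so this is a cheap improvement rather than a flaw that undermines the study. The text between 9.1.2 and 12.1 was not available to this review; if it describes contact after discharge, the point reduces to a wording conflict.

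**What to change.** Reconcile section 6, Table 1, 7.3.2 and 14.2 to one stated safety window. Table 1 already runs to day 14, so that window adds no visits. Say whether SAEs after it in patients still in hospital count towards 7.3.2, and align the event lists in 7.3.2 and 14.2.

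For patients discharged before the window closes, extend the chart review in 15.3 to them, covering readmission, death and recorded reactions. It must be done before the linking table is destroyed under 16.5, because records cannot be matched afterwards.

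State the denominator in section 13.2, report the number of patients with complete ascertainment alongside the cumulative incidence, and label any figure restricted to the stay as in-hospital.

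The cost is a wording change and one chart check per early-discharged patient. The remaining weakness is that events treated elsewhere may not appear in the chart, and the report should say so.
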